## **4.2 ANALYSIS OF STUDY CONDUCT**

Enrollment, infusion experience, discontinuation, and completion of the study will be summarized. Patient disposition and the incidence of treatment discontinuation for reasons other than disease progression will be tabulated. Pre-infusion medications and concomitant medications will be summarized. Major protocol violations, including violations of inclusion/exclusion criteria, will be listed.

## **4.3 ANALYSIS OF TREATMENT GROUP COMPARABILITY**

All patients will be treated in this study and treatment group comparability is not applicable. Instead, analysis will be conducted by the treatment cohort.

For continuous variables, the mean, median, SD, minimum, and maximum will be calculated. For categorical variables, number and percentage in each category will be displayed. The units/categories to be used are indicated within the brackets and separated by commas.

### **4.3.1 Demographics and Baseline Characteristics**

The following patient demographics and baseline characteristics will be summarized for the ITT population:

- Age (years)
- Age (years) group: (age categories  $\leq 40$ ,  $> 40$ , and age categories  $\geq 18$ -  $<40$ ,  $\geq 40$ - $\leq 55$ )
- Sex
- Self-reported race and ethnicity
- Baseline weight
- EDSS score
- EDSS category: (EDSS categories  $< 4$ ,  $\geq 4$ , and EDSS categories  $< 2.5$ ,  $\geq 2.5$ )
- Female fertility status
- MS type (RMS, PPMS)

Demographics and baseline characteristics will be summarized further by MS diagnosis categories (RMS, PPMS).

#### **4.3.2 Multiple Sclerosis Disease History**

MS medical history will be summarized by system organ classes and preferred terms for the safety population. A listing of medical history will also be provided by treatment cohort.

#### **4.4 EFFICACY ANALYSIS**

Not applicable.

#### **4.5 PHARMACOKINETIC AND PHARMACODYNAMIC ANALYSES**

Not applicable.

#### **4.6 SAFETY ANALYSES**

##### **4.6.1 Exposure to Study Medication**

Patients will receive only one infusion in this study. Patients will be considered to have received study medication even if the infusion was incomplete.

Descriptive statistics (n, mean, SD, median, minimum, maximum, 25th and 75th percentiles) of infusion duration (hours) and actual dose administered (mg and mL) and count and proportion of patients by infusion duration category (hours) ( $\leq 1.5$ ,  $>1.5$  to  $\leq 2$ ,  $>2$  to  $\leq 2.5$ ,  $>2.5$  to  $\leq 3$ ,  $>3$ ) will be tabulated.

Infusion start and stop date and time, total duration (hours), actual dose administered (mL), type of dose adjustment, and reason for infusion modification will be listed separately for all patients and for only those who experienced slowed, interrupted, or discontinued infusion.

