4.3.1 Study Treatment Formulation, Packaging, and Handling

4.3.1.1 Ocrelizumab

Ocrelizumab is a liquid formulation containing 30-mg/mL ocrelizumab in 20 mM sodium acetate at pH 5.3, with 4% trehalose dihydrate and 0.02% polysorbate 20. The drug product is a single-use liquid formulation in a 15-cc, type I USP, glass vial fitted with a 20-mm, fluoro-resin, laminated stopper and an aluminum seal with a flip-off plastic cap and contains a nominal 300 mg ocrelizumab. No preservative is used as each vial is designed for single use.

The ocrelizumab drug product must be diluted before administration. Solutions of ocrelizumab for IV administration are prepared by dilution of the drug product into an infusion bag containing 0.9% sodium chloride to a final drug concentration of 1 to 2 mg/mL.

Ocrelizumab may contain fine translucent and/or reflective particles associated with enhanced opalescence. Do not use the solution if discolored or if the solution contains discrete foreign particulate matter.

Administer the diluted infusion solution through a dedicated line using an infusion set with a 0.2 or 0.22 micron in-line filter.

The infusion solution must be administered using an infusion set with an in-line, sterile, non-pyrogenic, low-protein-binding filter (pore size of up to 0.2 micrometer).

The prepared infusion solution of ocrelizumab is physically and chemically stable for 24 hours at 2–8°C and subsequently 8 hours at room temperature. The prepared infusion solution should be used immediately. If not used immediately, it can be stored up to 24 hours at 2–8°C. Infusion solution must be completely administered to the patient within 32 hours of preparation (not exceeding 24 hours at 2–8°C and 8 hours at room temperature). In the event an IV infusion cannot be completed the same day, the remaining solution should be discarded.

For information on the formulation and handling of ocrelizumab, see the Ocrelizumab Investigator's Brochure.

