4.3.2 Study Treatment Dosage, Administration, and Compliance

The treatment regimen is summarized in Section 3.1.

Patients in Cohort 1 will receive 600-mg IV ocrelizumab per a shorter infusion protocol for Dose 2 or Dose 3. After their infusion, patients in Cohort 1 will have a brief telephone interview within 24 hours of the infusion to assess patient status. Patients will then continue to Safety Follow-up 30 days after their last dose of ocrelizumab and complete the study.

Patients in Cohort 2 will receive Dose 1 of ocrelizumab as 2 split 300-mg IV infusions 14 days apart. The first infusion will be administered per the U.S. label; the second infusion will be administered per a shorter infusion protocol. Patients will have a telephone call within 24 hours of infusion and then continue to Safety Follow-up 30 days after their last dose and complete the study.

For shorter infusion rates, see [Table 2](#) and [Table 3](#) below.

Table 2 Shorter Infusion Rates for 600-mg Ocrelizumab (Cohort 1)

Time (min)	Infusion rate (mL/hr)	Infusion rate (mg/hr)	Max Dose per Interval (mg)	Cumulative Dose (mg)
0–15	100	120	30	30
15–30	200	240	60	90
30–60	250	300	150	240
60–90	300	360	180	420
90–120	300	360	180	600

Infusion time: 120 min.

Preparation per U.S. label: 600 mg ocrelizumab/500 mL normal saline toward a drug concentration of approximately 1.2 mg/mL.

Table 3 Shorter Infusion Rates for 300-mg Ocrelizumab (Cohort 2, Infusion 2 of Dose 1)

Time (min)	Infusion rate (mL/hr)	Infusion rate (mg/hr)	Max Dose per Interval (mg)	Cumulative Dose (mg)
0–15	100	120	30	30
15–30	100	120	30	60
30–60	200	240	120	180
60–90	200	240	120	300

Infusion time: 90 min.

Preparation per U.S. label: 300 mg ocrelizumab/250 mL normal saline toward a drug concentration of approximately 1.2 mg/mL.

Although ocrelizumab may be administered on an outpatient basis, patients may be hospitalized for observation at the discretion of the investigator. Ocrelizumab infusions should always be administered in a hospital or clinic environment under close supervision of the investigator or a medically qualified staff member.

To reduce potential IRRs, all patients will receive prophylactic treatment with 100 mg of methylprednisolone (or equivalent steroid), to be completed approximately 30 minutes before the start of each ocrelizumab infusion, and with an antihistaminic drug (e.g., diphenhydramine) approximately 30–60 minutes before each ocrelizumab infusion.

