Refer to Section 5.1.1 and Section 5.1.2 for the risks associated with these mandatory premedications.

It is also strongly recommended that the infusion is accompanied by prophylactic treatment with an analgesic/antipyretic such as acetaminophen/paracetamol (1 g) 30–60 minutes prior to the start of an infusion to reduce potential IRRs.

Since transient hypotension may occur during ocrelizumab infusion, the investigator may wish to withhold anti-hypertensive medications 12 hours prior to ocrelizumab infusion.

Ocrelizumab must not be administered as an IV push or bolus. Well-adjusted infusion pumps should be used to control the infusion rate, and ocrelizumab should be infused through a dedicated line. It is important not to use evacuated glass containers, which require vented administration sets, to prepare the infusion because this causes foaming as air bubbles pass through the solution.

After completion of the infusion, the IV cannula should remain in situ for at least 1 hour to allow for administration of drugs intravenously, if necessary, in the event of a delayed reaction. If no adverse events occur during this period of time, the IV cannula may be removed and the patient may be discharged.

See the Ocrelizumab Investigator's Brochure for detailed instructions on drug preparation, storage, and approved administration.

Because of possible need to vary infusion rates depending on tolerance of the infusion, the total infusion time may exceed the time stated. **Unless an IRR occurs necessitating discontinuation, the entire contents of the infusion bag must be administered to the patient.**

Guidelines for treatment discontinuation are provided in Section 4.6.1.

Any overdose or incorrect administration of ocrelizumab should be noted on the Study Drug Administration electronic Case Report Form (eCRF). Adverse events associated with an overdose or incorrect administration of any of the study treatments should be recorded on the Adverse Event eCRF.

Guidelines for dosage modification and treatment interruption or discontinuation for patients who experience adverse events are provided in Section 5.1.3.4.

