## 2. **STUDY DESIGN**

This study is an open-label, non-randomized study to evaluate rate and severity of IRRs of ocrelizumab infused over a shorter time period than the approved administration rate in patients with Primary Progressive MS (PPMS) or Relapsing MS (RMS) in the U.S.

The study will have 2 cohorts:

- Cohort 1 will examine the effect of administering ocrelizumab per a shorter infusion protocol for Dose 2 or Dose 3 (Week 24 or 48 from the initial infusion). This cohort will consist of patients who have already received one or two doses of ocrelizumab according to the approved infusion protocol (i.e., per current U.S. label) and have reported no serious IRRs and who will then receive the next infusion of ocrelizumab at a higher rate in order to deliver 600 mg over the course of approximately 2 hours.

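### Do infusion-duration bands cut exactly at the planned 1.5 and 2 hours hide whether the shorter infusion was achieved?

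*SAP*

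**What the plan says.** SAP 4.6.1 (Exposure to Study Medication) describes infusion duration in two ways within one sentence. The first is a continuous summary, "Descriptive statistics (n, mean, SD, median, minimum, maximum, 25"th and 75th percentiles, of duration and of the dose actually given. The second is the "count and proportion of patients by infusion duration category (hours"), with bands ≤1.5, >1.5 to ≤2, >2 to ≤2.5, >2.5 to ≤3 and >3 hours. The section also lists start and stop times, duration, type of adjustment and reason, once for everyone and once "for only those who experienced slowed, interrupted, or discontinued infusion".

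The planned durations are in Protocol 4.3.2. Table 2 (600 mg, Cohort 1) ends with "Infusion time: 120 min" and Table 3 (300 mg, Cohort 2) with "Infusion time: 90 min". Both are approximate targets: SAP section 2 says Cohort 1 is to "deliver 600 mg over the course of approximately 2 hours". Neither document sets a tolerance.

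Elsewhere, SAP 4.3 says that analysis is done by cohort. SAP 4.6.2 gives the number and proportion of patients whose infusion was slowed, interrupted or discontinued because of an IRR, with an exact 95% interval, and summarises adverse events leading to infusion adjustment.

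**The concern.** The trial asks whether a 2-hour infusion is safe, so a reader wants to know how many infusions really took about 2 hours. With a cut exactly at the target, an infusion run to plan sits on a boundary. One extra minute moves it into the band that holds infusions slowed under Protocol Table 4.

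The protocol also gives some reason to expect small overruns. Section 4.3.1.1 says "Ocrelizumab is a liquid formulation containing 30-mg/mL ocrelizumab", so 600 mg is 20 mL and 300 mg is 10 mL. Section 4.3.2 says "the entire contents of the infusion bag must be administered to the patient" unless a reaction stops the infusion. If the drug were added to a full saline bag, every on-schedule infusion would run a few minutes past the cut.

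At stake would be the reading of the exposure table: compliant infusions could appear as longer than planned and be indistinguishable there from infusions slowed for a reaction.

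**Working it through.** **1. Planned times reproduced (Protocol Tables 2 and 3).** Volume = Σ(minutes × mL/h ÷ 60), and dose = volume × 1.2 mg/mL.

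- Cohort 1: 25 + 50 + 125 + 150 + 150 = 500 mL = 600 mg in 120 minutes.
- Cohort 2: 25 + 25 + 100 + 100 = 250 mL = 300 mg in 90 minutes.

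Both agree with the protocol.

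**2. Where an on-plan infusion falls.** Upper bounds are inclusive, so 120 minutes falls in >1.5 to ≤2 hours and 90 minutes in ≤1.5 hours. At 121 or 91 minutes the infusion moves up one band.

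**3. Where a slowed infusion falls.** Protocol Table 4 halves the rate for at least 30 minutes after a mild or moderate IRR. Take one 30-minute half-rate period:

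- Cohort 1, onset at 65 min: 225 mL given; then 150 mL/h × 0.5 h = 75 mL; the last 200 mL at 300 mL/h takes 40 min. Total 65 + 30 + 40 = 135 min.
- Cohort 1, onset at 110 min: the last 50 mL at 150 mL/h takes 20 min. Total 130 min.
- Cohort 2, onset at 25 min: 41.7 mL given; then 50 mL/h × 0.5 h = 25 mL; the last 183.3 mL at 200 mL/h takes 55 min. Total 25 + 30 + 55 = 110 min.

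I stepped the onset by 5 minutes (5 to 110 in Cohort 1, 22 times; 5 to 80 in Cohort 2, 16 times). I allowed the schedule to resume either by clock time or where the dose left off. The overrun is 10 to 20 minutes, most often exactly 15. Every one of these infusions falls in >2 to ≤2.5 hours (Cohort 1) or >1.5 to ≤2 hours (Cohort 2), and none in the band that holds on-plan infusions. The overlap is therefore one-sided: it affects only unmodified infusions that run over.

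**4. How many unmodified infusions could cross the cut.** With a normal spread, P(over) = Φ(mean overrun ÷ SD). The mean and SD are assumptions; the documents give neither.

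- Mean overrun 0: 50% for any SD.
- Mean overrun 2 to 4 min, SD 2 to 8 min: from Φ(2/8) = 60% to Φ(4/2) = 98%.
- Drug added to a full bag: 20 mL ÷ 300 mL/h = 4 min and 10 mL ÷ 200 mL/h = 3 min, so 124 and 93 min. With SD 5 or 3 min, Φ(4/5) = 79% or Φ(4/3) = 91% in Cohort 1, and Φ(3/5) = 73% or Φ(3/3) = 84% in Cohort 2.

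The full-bag figures depend on a preparation step that the protocol does not spell out. Tables 2 and 3 close exactly at 500 and 250 mL. A 520 mL bag would hold 600 ÷ 520 = 1.15 mg/mL, against a stated concentration of approximately 1.2. Detailed preparation is left to the Investigator's Brochure.

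**5. The obvious alternative, an on-plan band of plan ±15 minutes.** In the runs of step 3, the overrun is 15 minutes or less at 16 of 22 onset times (resuming where the dose left off) or 20 of 22 (resuming by clock) in Cohort 1, and at 14 of 16 in Cohort 2. That is 73%, 91% and 88% of onset times. Most once-slowed infusions would be labelled on plan, and the new cut would sit on their most common duration.

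**6. A tighter alternative, plan +10 minutes.** With mean overrun 0 and SD 5, unmodified infusions above the cut fall from 50% to 2.3%, but 15.9% of infusions slowed by 15 minutes then count as on plan. With mean overrun 4 and SD 5 the figures are 79% to 11.5%, and 3.6%. Any cut on duration alone trades one error for the other.

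**The case for a change.** The strongest case for a change is this. The primary objective concerns 600 mg given over 2 hours, and the safety population (SAP 4.1.2) keeps everyone who received any dose. The bands are the SAP's only specified count of patients by duration, yet no output states how many infusions finished within a tolerance of plan. Median and quartiles do not separate modified from unmodified infusions. Modifications made for reasons other than an adverse event appear only in listings. A Cohort 1 infusion stopped early at 100 minutes also shares the on-plan band. The remedy would cost only wording, since start and stop times are already recorded.

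These facts stand, and the band counts alone are a poor measure of adherence to the planned time. But the SAP does not ask the bands to do that job. It identifies modified infusions from recorded adjustments and reasons, which is more reliable than inferring them from elapsed time. A systematic overrun of a few minutes would show at once in the cohort median and quartiles. An infusion stopped early would show in the actual dose and in the listing of modified infusions. If a reader wants on-time completion split by modified or not, the listed data supply it without a prespecified category.

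**Conclusion.** No change is needed. Two cuts do coincide with the planned 90 and 120 minutes without a tolerance, and unmodified infusions that overrun slightly will share a band with infusions slowed once. Under assumed spreads this could affect half or more of the unmodified infusions (50% with symmetric variation, 60 to 98% with a mean overrun of 2 to 4 minutes and SD 2 to 8).

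The consequence is limited to how one descriptive row reads. The primary analysis counts patients with Grade 3 or 4 IRRs after the 600-mg shorter infusion, whatever its duration, and its interval, the secondary intervals and the sample-size table are untouched. The continuous summary, the listings and the IRR-related modification proportion show what happened to each infusion. As cut, the on-plan band also has a merit: once-slowed infusions that are completed stay out of it, whereas a ±15-minute band would take in most of them.

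This rests on reading the SAP 4.3 by-cohort rule as covering the exposure table and on modelling slowing as a single 30-minute half-rate period. Longer slowing would only move infusions further from plan.

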##### **4.6.2 Adverse Events**

Adverse event analyses will be generated by summarizing and listing treatment-emergent adverse events only. Treatment-emergent events are defined as those adverse events with an observed or imputed onset date on or after the start date of study treatment and up to 30 days after the last dose of study drug. Only where the most extreme intensity is greater than the initial intensity will events with an onset date prior to the start of study treatment (and with an end date on or after the start of study treatment) be considered treatment-emergent. An adverse event with a completely missing non-imputed start date will be assumed to be treatment-emergent unless the adverse event has a complete non-imputed end date that is prior to start of study treatment.

For each adverse event recorded, the term entered by the investigator describing the event (the “reported term”) will be assigned a standardized term (the “preferred term” [PT]) based on the Medical Dictionary for Regulatory Activities (MedDRA) Version 22.0. All adverse events will be mapped to PTs and body system organ class (BSOC). All analyses of adverse events data will be performed using the PTs unless otherwise specified.

**Ocrelizumab—Genentech, Inc.**  
11/Statistical Analysis Plan ML40638

All adverse events will be summarized by NCI CTCAE v4.0 grade, and tabulated by body system and PT for individual adverse events within each body system. Multiple occurrences of the same event within a patient will be counted once. Adverse events will be sorted by body system (in decreasing order of overall incidence) and then by PT (in decreasing order of overall incidence).

CTCAE V4.0 Grade 3 to 5 adverse events, serious adverse events, adverse events leading to treatment discontinuation, adverse events leading to infusion adjustment, treatment-related adverse events, and adverse events with a fatal outcome will be summarized. In addition, all serious adverse events and deaths will be listed as applicable. Serious adverse events will be defined as all serious adverse events including serious IRRs.

All IRRs will be included in the adverse event analyses. An IRR and its corresponding symptoms are collected on the electronic Case Report Form (eCRF). The symptom(s) of an IRR and the IRR itself may be of different intensities. As other symptoms can be recorded as free-text on the eCRF page, symptoms will be coded using MedDRA and summarized by PT.

IRRs are categorized by the time of the event occurring during the infusion and within 24 hours of completion of the infusion. The number and percentage of patients with at least one IRR will be presented by cohort and infusion (patients with multiple events within an infusion will count only once). In addition, the total number of IRRs will be summarized (multiple events will be counted). The total and percentage (based on the total number of patients with at least one IRR) will be summarized by most extreme intensity. The number of patients who experienced an IRR that led to slowing down, interruption, or discontinuation of study drug will be summarized.

Symptoms of IRRs and serious IRRs will also be listed.

For the primary analysis, the number and proportion of patients who experience Grade 3 or 4 IRRs following the 600-mg shorter infusion will be provided with a 2-sided 95% exact Clopper-Pearson CI of the proportion.

For secondary analyses, the number and proportion of patients who experience Grade 1–4 IRRs following the 600-mg shorter infusion and the 300-mg shorter infusion, and the number and proportion of patients who experience Grade 3 or 4 IRRs following the 300-mg shorter infusion will be provided with a 2-sided 95% exact Clopper-Pearson CI of the proportion.

The number and proportion of patients who require slowing, interruption, or discontinuation of ocrelizumab due to IRRs following the 300-mg or 600-mg shorter infusion will be provided with a 2-sided 95% exact Clopper-Pearson CI of the proportion. In addition, the number and proportion patients with local and/or systemic infusion site

**Ocrelizumab—Genentech, Inc.**  
12/Statistical Analysis Plan ML40638

reactions will be summarized. Listings of infusion related reactions will be presented separately for all patients and for only those patients for whom the IRR led to infusion slowing down, interruption, and discontinuation.

#### **4.6.3        Laboratory Data**

Not applicable.

#### **4.6.4        Vital Signs**

Baseline, post-baseline, and change from baseline in vital signs will be summarized. Baseline for vital signs is defined as the last measurement prior to pre-infusion medication at Day 1 for both cohort 1 and cohort 2.

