3. STUDY DESIGN

3.1 DESCRIPTION OF THE STUDY

[figure not shown]
This study is an open-label, non-randomized study to evaluate rate and severity of IRRs of ocrelizumab infused over a shorter time period than the approved administration rate in patients with PPMS or RMS in the U.S. The study will have 2 cohorts:

- Cohort 1 will examine the effect of administering ocrelizumab per a shorter infusion protocol for Dose 2 or Dose 3 (Week 24 or 48 from the initial infusion). This cohort will consist of patients who have already received one or two doses of ocrelizumab according to the approved infusion protocol (i.e., per the currently U.S. label) and have reported no serious IRRs and who will then receive the next infusion of ocrelizumab at a higher rate in order to deliver 600 mg over the course of approximately 2 hours.
- Cohort 2 will examine the effect of administering ocrelizumab per a shorter infusion protocol for the second infusion of Dose 1. This cohort will consist of ocrelizumab-naïve patients who, after receiving Infusion 1/Dose 1 of ocrelizumab at the approved rate (300 mg over approximately 2.5 hours or longer) have no reported serious IRRs, will then receive the second 300-mg shorter infusion over approximately 1.5 hours.

All patients will have two safety follow-up telephone calls: the first within 24 hours of the ocrelizumab infusion and the second 30 days after their last ocrelizumab dose.

[figure not shown]
Figures 1 and 2 present the study overview by Cohort 1 and Cohort 2. A schedule of activities is provided in Appendix 1 for Cohort 1 and Appendix 2 for Cohort 2.

Figure 1 Study Schema: Cohort 1

Note: For Cohort 1, Dose 1 will be received prior to study enrollment per standard of care. Day 1 may occur at Week 24 or 48, depending on the previous treatment cycle.

Figure 2 Study Schema: Cohort 2

Note: For Cohort 2, Day 1 of Dose 1 is per standard of care.

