 - ^b Written informed consent will be obtained from all patients in order to be eligible for the study and prior to any study procedures.
 - ^c Medical history includes clinically significant diseases, surgeries, reproductive status, smoking history, and all medications (e.g., prescription drugs, over-the-counter drugs, herbal or homeopathic remedies, and nutritional supplements) used by the patient within 4 weeks prior to the visit. Demographic data will include age, sex, and self-reported race/ethnicity.
 - ^d A physical examination may be conducted, per standard of care. Any abnormality identified should be recorded on the eCRF. New or worsened clinically significant abnormalities should be recorded as adverse events, if appropriate.
 - ^e Vital signs will include the measurements of heart rate, systolic and diastolic blood pressures, and temperature. Vital signs should be taken approximately 45 minutes prior to the premedication methylprednisolone infusion. In addition, vital signs should be obtained prior to the ocrelizumab infusion then approximately every 15 minutes for the first hour, followed by approximately every 30 minutes until 1 hour after the end of the infusion.
 - ^f EDSS does not need to be performed if results within 6 months are available.
 - ^g On infusion visits, a urine pregnancy test must be performed prior to premedication in all women of childbearing potential. If a urine pregnancy test is positive, it must be confirmed by a serum pregnancy test. Ocrelizumab must be withheld until pregnancy status is confirmed.
 - ^h After informed consent has been obtained but prior to initiation of study drug, only serious adverse events caused by a protocol-mandated intervention (e.g., invasive procedures such as biopsies, discontinuation of medications) should be reported. After initiation of study drug, related serious adverse events must be collected and reported regardless of the time elapsed from the last study drug administration, even if the study has been closed. Unrelated serious adverse events must be collected and reported during the study and Safety Follow-up. Non-serious adverse events have to be reported until the end of Safety Follow-up.
 - ⁱ Medications used after treatment discontinuation should be recorded during Safety Follow-up.

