**Ocrelizumab—Genentech, Inc.**  
18/Statistical Analysis Plan ML40638

## Appendix 2 Schedule of Activities: Cohort 1

	Screening (Up to 28 days prior to Day 1)	Treatment Visit (Day 1) a	Telephone Call (24 hours after infusion)	Safety Follow-up (Day 30) b
Informed consent c	x			
Medical history and demographic data d	x			
Review inclusion and exclusion criteria	x			
Physical examination e	x			
Vital signs f		x		
EDSS	(x) g			
Hematology	x			
Pregnancy test h		x		
Adverse event assessment i			x	x
Concomitant treatment review	x	x		x j
Methylprednisolone and antihistamine premedication k		x		
Ocrelizumab administration		x l		

eCRF=electronic Case Report Form; EDSS=Expanded Disability Status Scale; IRR=infusion-related reaction; IV=intravenous.

a Day 1 may occur at Week 24 or 48, depending on the previous treatment cycle.

b Patients who receive ocrelizumab in this study or who discontinue from treatment or the study early, should enter the Safety Follow-up Period and be assessed 30 days counting from the date of their last ocrelizumab infusion via telephone.

c Written informed consent will be obtained from all patients in order to be eligible for the study and prior to any study procedures.

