- k All patients must receive prophylactic treatment with 100 mg methylprednisolone (or equivalent), to be completed approximately 30 minutes before the start of each ocrelizumab infusion, and with an antihistaminic drug (e.g., diphenhydramine) approximately 30–60 minutes before each infusion of ocrelizumab. Prophylactic treatment with an analgesic/antipyretic (e.g., 1 g acetaminophen) is strongly recommended 30–60 minutes prior to the start of ocrelizumab infusion to reduce the risk of IRRs.
- l Ocrelizumab will be administered as one 600-mg IV infusion over the course of approximately 2 hours (shorter infusion) for Infusion 2 or 3, depending on how many prior doses the patient has received.
-

### Appendix 3 Schedule of Activities: Cohort 2

	Screening (Up to 28 days prior to Day 1)	Treatment Visit (Day 15)	Telephone Call (24 hours after infusion)	Safety Follow-up (Day 30) a
Informed consent b	x			
Medical history and demographic data c	x			
Review inclusion and exclusion criteria	x			
Physical examination d	x			
Vital signs e		x		
EDSS	(x) f			
Hematology	x			
Pregnancy test g		x		
Adverse event assessment h			x	x
Concomitant treatment review	x	x		x i
Methylprednisolone and antihistamine premedication j		x		
Ocrelizumab administration		x k		

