**Ocrelizumab—Genentech, Inc.**  
21/Statistical Analysis Plan ML40638

---

eCRF=electronic Case Report Form; EDSS=Expanded Disability Status Scale; IRR=infusion-related reaction; IV=intravenous.

- a Patients who receive ocrelizumab in this study or who discontinue from treatment or the study early, should enter the Safety Follow-up Period and be assessed 30 days counting from the date of their last ocrelizumab infusion via telephone.
  - b Written informed consent will be obtained from all patients in order to be eligible for the study and prior to any study procedures.
  - c Medical history includes clinically significant diseases, surgeries, reproductive status, smoking history, and all medications (e.g., prescription drugs, over-the-counter drugs, herbal or homeopathic remedies, and nutritional supplements) used by the patient within 4 weeks prior to the visit. Demographic data will include age, sex, and self-reported race/ethnicity.
  - d A physical examination may be conducted, per standard of care. Any abnormality identified should be recorded on the eCRF. New or worsened clinically significant abnormalities should be recorded as adverse events, if appropriate.
  - e Vital signs will include the measurements of heart rate, systolic and diastolic blood pressures, and temperature. Vital signs should be taken approximately 45 minutes prior to the premedication methylprednisolone infusion. In addition, vital signs should be obtained prior to the ocrelizumab infusion then approximately every 15 minutes for the first hour, followed by approximately every 30 minutes until 1 hour after the end of the infusion.
  - f EDSS does not need to be performed if results within 6 months are available.
  - g On infusion visits, a urine pregnancy test must be performed prior to premedication in all women of childbearing potential. If a urine pregnancy test is positive, it must be confirmed by a serum pregnancy test. Ocrelizumab must be withheld until pregnancy status is confirmed.

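### The SAP sets the vital-sign baseline at Day 1 in both cohorts, but Cohort 2 has its study infusion and all its scheduled vital signs on Day 15

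*SAP*

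**What the plan says.** SAP 4.6.4 (Vital Signs) plans summaries of baseline, post-baseline and change from baseline, and gives one rule for both cohorts: "Baseline for vital signs is defined as the last measurement prior to pre-infusion medication at Day 1 for both cohort 1 and cohort 2". SAP 2.2.3 lists change from baseline in vital signs among the safety outcome measures.

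The schedules number the days differently in the two cohorts:

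- **Cohort 1** (SAP Appendix 2; Protocol Appendix 1). The treatment visit is Day 1. Footnote a adds: "Day 1 may occur at Week 24 or 48, depending on the previous treatment cycle". Day 1 is therefore the study infusion, wherever it falls in the patient's treatment history.
- **Cohort 2** (SAP Appendix 3; Protocol Appendix 2). The treatment visit is Day 15. The vital-signs row has one mark, in that column. Screening is counted back from Day 1, but Day 1 has no visit column.

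The note to Figure 2 in Protocol 3.1 explains what that Day 1 is: "For Cohort 2, Day 1 of Dose 1 is per standard of care". Protocol 4.3.2 gives the spacing: "Patients in Cohort 2 will receive Dose 1 of ocrelizumab as 2 split 300-mg IV infusions 14 days apart". The second of these two infusions is the shorter one.

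**The concern.** The rule uses one day label for two different events. In Cohort 1 it selects the reading just before the infusion under study. In Cohort 2 it points to the day of an infusion given at the approved rate before the one under study, when the study schedules no vital signs.

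A change from baseline around an infusion is meant to show what happens to blood pressure, pulse and temperature once that infusion starts. This needs a reference value from the same day. If the Cohort 2 rule is programmed literally, baseline and every change value are missing. If the programmer looks for a reading taken on Day 1 in routine care, the change spans two weeks and an extra infusion with its premedication. If the programmer assumes Day 15 was meant, the result is sensible but rests on a decision that the SAP does not record. The protocol names hypotension and tachycardia as ways in which an infusion-related reaction can present, so these summaries have some safety relevance.

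**Working it through.** This is mainly a cross-check of the text. The plan gives no figure for the number of vital-sign readings. The one figure that can be reproduced is the interval between infusions: Day 15 − Day 1 = 14 days, which agrees with Protocol 4.3.2.

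**Does any scheduled reading meet the rule?**

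| | Cohort 1 | Cohort 2 |
|---|---|---|
| Study (shorter) infusion | Day 1 | Day 15 |
| Vital signs marked at | Day 1 | Day 15 only |
| Vital signs at screening | none | none |
| Scheduled reading before premedication on Day 1 | yes | no |
| Scheduled reading before premedication on the study-infusion day | yes | yes |

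The last row relies on footnote e of the Cohort 2 schedule (Protocol Appendix 2, repeated in SAP Appendix 3): "Vital signs should be taken approximately 45 minutes prior to the premedication methylprednisolone infusion". The right baseline value is therefore already collected; the rule points to a different day. No screening reading is scheduled that could stand in.

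**How many values are affected?**

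Inputs:
- Cohort sizes 100 and 50 (SAP 2.3).
- Infusion times of 120 minutes in Cohort 1 (Protocol Table 2) and 90 minutes in Cohort 2 (Protocol Table 3: "Infusion time: 90 min").
- One reading before premedication, one before the infusion, and later ones on the timetable in footnote e: "approximately every 15 minutes for the first hour, followed by approximately every 30 minutes until 1 hour after the end of the infusion".

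Assumptions: no infusion is slowed, data are complete, and a change is calculated at every reading after the start.

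Cohort 2, 90-minute infusion, monitored to 90 + 60 = 150 minutes:
- Before the start: 1 before premedication + 1 before infusion = 2.
- After the start: 4 (at 15, 30, 45, 60 minutes) + 3 (at 90, 120, 150 minutes) = 7.
- Day 15 total: 2 + 7 = 9. Day 1 total: 0.
- Change values per vital sign: 7 × 50 = 350.

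Cohort 1, 120-minute infusion, monitored to 120 + 60 = 180 minutes:
- After the start: 4 + 4 (at 90, 120, 150, 180 minutes) = 8.
- Change values per vital sign: 8 × 100 = 800.

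Shares: 350 / (350 + 800) = 350 / 1,150 = 30% of planned change values, and 50 / 150 = 33% of patients.

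**The case against.** The best defence is that Day 1 simply means the day of study treatment. SAP 4.6.1 says that each patient has a single infusion in the study, and SAP 4.6.2 dates adverse events from the start of study treatment. The Cohort 2 schedule is not on one strict clock either: its Day 30 follow-up is counted from the last infusion, which would be about Day 45 (15 + 30) counted from the first infusion. A programmer who looks for a scheduled Cohort 2 reading before premedication finds only one, so the sensible answer is close at hand.

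Further points deserve weight. Protocol 4.5.4 names no day for vital signs, and Figure 2 is not visible in the text available, so Day 1 readings in routine care cannot be ruled out; the documents do not say that any are collected. The SAP schedule does not itself state that the Cohort 2 Day 1 is the first infusion; the protocol note does. SAP 4.6.4 names no post-baseline time points, so the count of 350 is only indicative.

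Most of this stands, and it makes the study-infusion day the likely intent. It does not remove the conflict. No section of the SAP defines Day 1 as the study-infusion day. The rule names Cohort 2 expressly, and the SAP's own Cohort 2 schedule numbers the study infusion Day 15 while counting screening from a separate Day 1.

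**Conclusion.** The point holds, at minor severity. As written, the baseline rule gives Cohort 2 either no scheduled baseline or, if unscheduled readings were used, one taken 14 days and one infusion before the infusion under study.

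It reaches the 50 planned Cohort 2 patients and, under the assumptions above, about 350 planned change values per vital sign. These figures show how many values lack a clear reference point. They say nothing about the size or direction of any error, and there is none if the Day 15 reading is used.

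The consequences are limited. The affected summaries are descriptive and carry no test or decision rule. Clinically significant vital-sign abnormalities are recorded separately as adverse events under Protocol 5.3.5.6. The primary and secondary proportions of patients with infusion-related reactions, and their confidence intervals, do not depend on this definition.

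**What to change.** Replace the baseline sentence in SAP 4.6.4 with: *Baseline is the last measurement before premedication on the day of the shorter infusion (Day 1 in Cohort 1, Day 15 in Cohort 2).*

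The cost is one sentence in the SAP. The reading is already required at the Day 15 visit, so no data, visits or patients are added. If the sponsor always meant this, the change only records it.
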